## Run-in Phase

We will conduct a “run-in” of the EICI in each of the participating hospitals with 10 women and then will conduct a follow up interview with all of these participants.

## Inclusion and Exclusion Criterion

Inclusion criteria for the intervention include: adult ( $\geq 18$  years) English speaking women who are already being approached for participation in the BioTrust.

Exclusion criteria include mothers of infants that are in the NICU and any situation adoption or legal guardianship is unknown at the time of birth.

## Recruitment

Our research procedures are designed to mirror the current practice at the individual hospitals as much as possible. Typically, nurses discuss the BioTrust informational brochure shortly after moving into the Mother & Baby unit as part of the packet of information related to their stay in the unit. Once the baby is 24 hours old, the nursery tech comes to complete newborn screening and asks for BioTrust consent at that time.

Our approach will use a full time research assistant (RA) at each hospital. All potential participants will receive the brochure as part of standard practice during their welcome to the Mother & Baby Unit. At some point after admission to the Unit, the RA will approach the patient, briefly describe the study and content of data collected, and seek verbal consent for participation in the study. If they consent, the RA will activate the study-provided electronic tablet to see the study group assignment; study staff and healthcare providers will be blind to the study group assignment until this point. Participants will be randomized into the video intervention group (Group A), interactive intervention group (Group B), or standard of care group (Group C). The patient will then complete the intervention (Groups A and B) or continue the BioTrust discussion with the nurse (Group C).

## Intervention Groups A and B

Following randomization, participants in Groups A or B will be given the electronic tablet with the intervention loaded on the screen and provided with instructions. In order to allow participants as much time as necessary to explore the app, the RA will leave the room while the patient is working on the tablet and return within an hour to pick up the tablet. Participants in Group A will be asked to watch a 6-minute video about what it means to consent to have the NBS bloodspots retained by the Michigan BioTrust. Participants in Group B will be provided with the same information in an interactive app form, and will be asked to explore the informational sections at their preferred level of depth. After the video ends or participants

reach the end point of the educational app, they will automatically be directed to complete the associated questionnaires. When the RA returns, she will collect the tablet and provide the participant with a \$25 gift card to Amazon. The next day, the Nursery Tech will visit the patient's room to gather NBS bloodspots and consent for the BioTrust, following the **standard consent process**.

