### Control Group C

Participants who are randomized to Group C will complete the questionnaires immediately following the BioTrust discussion with the nurse. The RA will stay in the room while the surveys are being completed then provide the participant with a \$25 gift card to Amazon. The next day, the Nursery Tech will visit the patient's room to gather NBS bloodspots and consent for the BioTrust, following the **standard consent process**. The RA will review collected consent cards to document the patient's choice to consent or deny.

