### Survey Tools

All participating women will complete a survey 1) immediately following the intervention/control on the electronic tablet and 2) by telephone 2-4 weeks follow up. Participants will receive an additional \$25 gift card to Amazon after the follow-up survey.

Outcome measures include:

- knowledge of the elements of consent and key aspects of the biobank
- decisional conflict
- satisfaction with the consent process and attitudes toward the clinical program the samples were collected for and research with these samples
- rates of parental permission

We will also collect demographic information on the participants and contact information for contact by telephone 2-4 weeks later. All identifying information will be kept in a secure data storage system separate from data used for analyses.

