### Analysis Plan

Summary statistics for baseline demographics (age, ethnicity, race, income, etc.) will be calculated and reported for each intervention group (App or Video) versus Control. We will utilize multilevel generalized mixed modeling (via SPSS and R) under an intent-to-treat (ITT) approach to compare primary, secondary outcomes, and exploratory outcomes.

**Hypothesis Testing:** To evaluate the fixed effect of the two different groups upon knowledge we will utilize a single level model that includes the fixed effect of group (G).

$$Y_i = [\gamma_0 + \gamma_1 G_i] + [\zeta_i + \epsilon_i]$$

where Y is the composite score for knowledge. G is an indicator for the different groups (App or Video, Control). We will set alpha = 0.05. The two group model reduces to a 2 sided, t-test approach.

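### The in-hospital questionnaires are answered with the RA out of the room in Groups A and B but in the room in Group C, so measurement conditions are confounded with intervention versus control

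*Combined protocol and SAP*

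**What the plan says.** The section on Intervention Groups A and B has the RA hand over the tablet and go: "the RA will leave the room while the patient is working on the tablet and return within an hour to pick up the tablet". The reason given is to allow enough time with the app. Once the video or app is finished, "they will automatically be directed to complete the associated questionnaires", so the questionnaires belong to the same unattended session. The next RA action described is retrieval: "When the RA returns, she will collect the tablet".

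The section on Control Group C differs. Participants "will complete the questionnaires immediately following the BioTrust discussion with the nurse", and "The RA will stay in the room while the surveys are being completed". No reason is given for staying.

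Survey Tools describes one in-hospital survey for all women, taken "immediately following the intervention/control on the electronic tablet", followed by a telephone survey at 2-4 weeks. The only written test is for knowledge, in the Analysis Plan: "we will utilize a single level model that includes the fixed effect of group (G"). That section does not say whether the knowledge score comes from the in-hospital or the telephone survey.

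**The concern.** An outcome should be measured in the same way in every arm. Here the presence of a study staff member during measurement changes with the arm, and the change falls exactly between intervention and control. The stated reason for leaving concerns the education step and does not extend to the questionnaires.

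The bias could run in either direction:

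- **Towards A and B.** Unattended participants can look up answers or be helped. Under Recruitment, "All potential participants will receive the brochure as part of standard practice", and a partner may be present in any arm. The Partners section reports fathers in the room in roughly half of observed consent encounters and actively involved in two thirds of those, which is about one third of encounters (1/2 × 2/3). Brochure and partner are available in all arms; what differs is whether the RA is there to see them used.
- **Towards C.** With the RA in the room, participants may concentrate harder or ask the RA for help, which would raise knowledge scores. Decisional conflict, satisfaction and attitudes may shift through socially desirable answering.

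At stake is whether a difference between an intervention arm and control on the in-hospital survey, or the lack of one, can be attributed to the intervention.

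**Working it through.** **1. The procedures side by side.**

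| Step | Groups A and B | Group C |
|---|---|---|
| Before the survey | Video or app on the tablet | Discussion with the nurse |
| Start of the survey | Automatic, at the end of the video or app | Right after the discussion |
| RA during the survey | Out of the room, back within an hour | In the room |
| Permission decision | Standard process, next day | Standard process, next day |

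The first row is the treatment contrast that the trial is meant to test. The third row is a feature of measurement and not part of any intervention.

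**2. Can the analysis separate the two?** Code RA presence as 1 in Group C and 0 in Groups A and B. The design matrix for three groups (intercept and two indicators) has rank 3, and adding RA presence leaves it at 3. For A and B combined versus C the rank is 2 and stays at 2. RA presence is fully aliased with intervention versus control. This is not a fault of the Analysis Plan: no added covariate could help, and only a change in conduct can.

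**3. What a shift would do.** The documents give no sample size, effect size or SD, so there is no planned figure to reproduce. From the plan: alpha 0.05, two-sided. Assumed: SD = 1, n per arm, true effect d, and a shift b caused by the setting, for one intervention arm versus control.

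Rejection probability = Φ((d + b)/SE − 1.96) + Φ(−(d + b)/SE − 1.96), with SE = √(2/n).

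SE is √(2/100) = 0.1414 at n = 100 and √(2/200) = 0.1000 at n = 200. For example, with n = 100, d = 0 and b = 0.2, the shift is 0.2/0.1414 = 1.414 standard errors, and Φ(−0.546) + Φ(−3.374) = 0.293.

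No true effect (d = 0); the result is the same for either sign of b:

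| n per arm | b = 0 | b = ±0.1 | b = ±0.2 |
|---|---|---|---|
| 100 | 0.050 | 0.109 | 0.293 |
| 200 | 0.050 | 0.170 | 0.516 |

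True effect present, shift favouring Group C:

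| n per arm | d | b = 0 | b = −0.1 | b = −0.2 |
|---|---|---|---|---|
| 100 | 0.4 | 0.807 | 0.564 | 0.293 |
| 200 | 0.3 | 0.851 | 0.516 | 0.170 |

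A shift favouring A or B would instead inflate the apparent effect. A true effect much larger than b would still be detected, but its estimate would be off by b.

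**The case against.** The strongest reply is about scope. The one written test may use the telephone score, for which no arm difference in RA presence is described; in that case the tested outcome is measured under equal conditions. This stands as a limit: the concern covers the in-hospital survey only. It is not a safeguard, because the plan does not say which survey supplies the score.

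Second, the text says that the RA is in the room, not that the RA watches or helps, and the survey is self-completed on a tablet. The mechanisms above are therefore conjecture. That is correct, and it is why no size or direction is claimed. The difference in conditions is documented all the same.

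Third, absence throughout the questionnaires in A and B is inferred from the order of events. An RA who comes back early may find a participant still answering. That would weaken the contrast without removing it.

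Fourth, the arms also differ in what comes just before the survey: a live conversation or a tablet session. Equal RA presence would not make the settings identical. True, but that difference belongs to the comparison being tested, whereas RA presence during measurement does not.

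Finally, the rejection rates would follow from any bias of the same size and say nothing specific about RA presence. They show only what such a bias would cost.

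**Conclusion.** The concern holds. If the plan is followed as written, RA presence during the in-hospital questionnaires is confounded with intervention versus control, for knowledge, decisional conflict, satisfaction and attitudes, and no analysis can undo this.

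The procedural difference is clear from the text; the bias it causes is of unknown size and sign. The illustrative figures rest entirely on assumed shifts, effects and sample sizes. The A versus B comparison is unaffected because both arms follow the same procedure, and permission rates are unaffected because consent is sought the next day in the same way in every arm. The telephone survey is not shown to be affected. This should be fixed, chiefly because a simple change removes a problem that cannot be repaired later.

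**What to change.** Set one RA-presence rule for the questionnaire step in all three arms. The simplest form is to amend the Control Group C section so that, after the nurse discussion, the RA hands over the tablet and leaves while the questionnaires are answered, as in A and B. Having the RA come back for the questionnaires in A and B would also equalise conditions, but it is harder to run because Group B participants decide when they reach that step.

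Have the tablet log start and stop times of the questionnaire step in every arm. If a time limit is wanted, apply it to that step alone and make it equal across arms; the hour in A and B is the RA's return time and also covers the video or app, so it should not be carried over to Group C. If conditions cannot be equalised, state the difference as a limitation and give weight to the telephone survey.

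The cost is a wording change and a time log, with no extra staff, visits or participants. The downside is less prompting, and perhaps slightly lower completion, in Group C. Looking up answers would then be equally possible in every arm, not prevented.

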### Control Group C

Participants who are randomized to Group C will complete the questionnaires immediately following the BioTrust discussion with the nurse. The RA will stay in the room while the surveys are being completed then provide the participant with a \$25 gift card to Amazon. The next day, the Nursery Tech will visit the patient's room to gather NBS bloodspots and consent for the BioTrust, following the **standard consent process**. The RA will review collected consent cards to document the patient's choice to consent or deny.

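### Is the BioTrust permission decision recorded in the control arm only, because consent-card review is written only under Control Group C?

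*Combined protocol and SAP*

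**What the plan says.** Recruitment describes three randomised groups: video (A), interactive app (B) and standard of care (C). It also states the staffing: "Our approach will use a full time research assistant (RA) at each hospital".

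Under Intervention Groups A and B, the last task written for the research assistant is: "When the RA returns, she will collect the tablet and provide the participant with a" gift card. The decision itself comes later: "The next day, the Nursery Tech will visit the patient's room to gather NBS bloodspots and consent for the BioTrust", under the hospital's standard process.

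Control Group C repeats that consent-visit sentence and then adds one more: "The RA will review collected consent cards to document the patient's choice to consent or deny". Consent cards are mentioned nowhere else in the sections from Run-in Phase to Analysis Plan.

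Survey Tools lists "rates of parental permission" as an outcome with no limit to any arm. The Analysis Plan intends to compare primary, secondary and exploratory outcomes by intention to treat, but writes out a model for knowledge only. Permission is given no tier, hypothesis or model of its own.

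**The concern.** A randomised comparison of permission needs the decision to be ascertained in the same way in every arm. If staff took each arm section as a complete and separate instruction, they would transcribe consent cards for Group C and have no written instruction to do so for Groups A and B. The permission rate in A and B would then be missing, or would come from another source such as the telephone call 2 to 4 weeks later. A card record in one arm set against recall among those reached by telephone in the other two would be differential ascertainment, of unknown size and direction.

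The surveys do not plainly close the gap. The timing of the first is given as "All participating women will complete a survey 1) immediately following the intervention/control on the electronic tablet", and the consent visit is a day later, so that survey cannot contain the actual choice. The telephone survey could ask for it, but none of the sections says that it does.

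**Working it through.** There is no figure to reproduce. The available sections give no sample size, permission rate or effect size for this outcome, so the check is a comparison of text.

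**Counts over the nine sections from Run-in Phase to Analysis Plan**

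| Item | Groups A and B section | Group C section | Coverage |
|---|---|---|---|
| Next-day consent visit | yes | yes | 2 of 2 sections, 3 of 3 arms |
| Card review by the research assistant | no | yes | 1 of 2 sections, 1 of 3 arms |
| Research assistant tasks after the consent visit | 0 | 1 | |

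Statements that either survey asks what was decided: 0 of 9 sections. The survey instruments are not reproduced, so this is silence and does not show that the question is absent.

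**What the counts support.** The card sentence is written once, under one arm. That much is fact. Whether it governs only that arm has to be read from its wording and surroundings.

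1. *Wording.* The Group C section opens by naming participants randomised to that group. The card sentence names no group and speaks of the patient in general.
2. *Position.* It is the last sentence of the arm-by-arm procedures and follows a consent-visit sentence identical to the one for Groups A and B. A closing remark meant for all arms would naturally fall there.
3. *What is reviewed.* The cards are described as already collected. Collection belongs to the routine consent process, which both arm sections say is followed. The natural inference is that a card exists for participants in every arm, whether or not the research assistant looks at it. On the strict reading, what is missing for A and B is a transcription instruction; the decision itself would still be on record.
4. *Purpose.* The permission outcome carries no arm restriction, and the Analysis Plan compares outcomes between groups. A review confined to the control arm would yield a rate with no comparator.
5. *Participant consent.* At recruitment the research assistant will "briefly describe the study and content of data collected, and seek verbal consent for participation in the study" before the tablet reveals the assignment. The description of what will be collected is therefore given before anyone knows the arm, which fits card review in all arms better than review in one.
6. *Resources.* With a full-time research assistant at each hospital, nothing in the plan suggests that A and B were left out to save effort.

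**Effect of the strict reading on the stated analyses.** The knowledge model contains group and the knowledge score only. Card review enters neither term, so the estimate and its two-sided test at alpha 0.05 stay the same under either reading.

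**The case for a change.** The best argument for a change is the document's own drafting habit. Steps shared by the arms are repeated in each section: the gift card and the whole consent-visit sentence appear in both. By that convention a step written once looks specific to its section, and a research assistant who consulted only the text for Groups A and B would find no instruction to look at a card. The documents also do not say how long cards stay accessible, so a choice left untranscribed might be harder to recover later. The remedy would be a single sentence.

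The drafting point stands, and the text is ambiguous as written. It does not show that ascertainment would differ. For that to happen, the team would have to pass over an outcome listed for all participants and a planned comparison between groups. The same research assistants serve all three arms, and the plan has them meet with the research director at least weekly, so a missing permission record in two arms out of three would be expected to surface quickly. Nothing suggests that the cards would be lost.

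An amendment naming the card as the sole permission source would also go further than the text supports. Permission is listed under Survey Tools beside measures such as "satisfaction with the consent process and attitudes toward the clinical program the samples were collected for and research with these samples", so a survey source common to all arms has not been ruled out.

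**Conclusion.** The concern does not call for a change. The sentence on card review is placed under one arm although its wording and purpose fit all three. This is a gap of placement that staff and analysts would fill in the obvious way, by reading cards in Groups A, B and C alike. Writing that down would record what the trial would almost certainly do anyway, and would alter no number, model or conclusion stated in the plan.

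The size is one sentence, affecting one outcome that has no stated tier or hypothesis. No bias can be quantified from the documents, and none is shown to exist.

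The conclusion rests on three assumptions: that the standard consent process leaves a card for participants in every arm, which the text implies but does not state; that those cards can be reached during the trial; and that the part of the document before Run-in Phase, which was not available for this check, does not confine card review to the control arm. If the last proved false, the concern would have to be reopened.

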### Survey Tools

All participating women will complete a survey 1) immediately following the intervention/control on the electronic tablet and 2) by telephone 2-4 weeks follow up. Participants will receive an additional \$25 gift card to Amazon after the follow-up survey.

Outcome measures include:

- knowledge of the elements of consent and key aspects of the biobank
- decisional conflict
- satisfaction with the consent process and attitudes toward the clinical program the samples were collected for and research with these samples
- rates of parental permission

We will also collect demographic information on the participants and contact information for contact by telephone 2-4 weeks later. All identifying information will be kept in a secure data storage system separate from data used for analyses.

### Partners

Research indicates that the partners of pregnant women are typically not *approached* for consent for the retention of specimens in the biorepository. Our Process Observations revealed that fathers were in the room during the consent process in roughly half of the cases and were vocal and involved in the process in two thirds of those situations. Therefore we will not attempt to recruit those who are in the hospital although partners will be welcomed to participate in the intervention if they are present. The role of partners may be important in decision-making about biobanking whether or not they are typically approached. All participants will be asked in the 2-4 week follow-up survey about the role of their partner in decision-making about specimen biobanking. Additionally, whoever completed the survey in the hospital will be the same person to complete the 2-4 week survey, regardless of status as birth mother or partner.

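### Does letting a partner answer the surveys undermine the comparison of the groups?

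*Combined protocol and SAP*

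**What the plan says.** All sections named here belong to the combined protocol and SAP.

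- **Inclusion and Exclusion Criterion** limits enrolment to adult "English speaking women who are already being approached for participation in the BioTrust".
- **Recruitment** is directed at the same person: "the RA will approach the patient, briefly describe the study and content of data collected, and seek verbal consent for participation".
- **Survey Tools** states: "All participating women will complete a survey 1) immediately following the intervention/control on the electronic tablet", with a second survey by telephone at 2-4 weeks. On storage it adds: "All identifying information will be kept in a secure data storage system separate from data used for analyses".
- **Partners** says of partners: "Therefore we will not attempt to recruit those who are in the hospital". It lets a partner who is present share in the intervention. It then makes whoever answered in hospital "the same person to complete the 2-4 week survey, regardless of status as birth mother or partner". Participants are also "asked in the 2-4 week follow-up survey about the role of their partner in decision-making about specimen biobanking".
- **Intervention Groups A and B** has the research assistant (RA) leave the room while the tablet is in use. **Control Group C** has the RA stay during the questionnaires, and on permission it says: "The RA will review collected consent cards to document the patient's choice to consent or deny".
- **Analysis Plan** compares outcomes by intent to treat and models the knowledge score with group as the only fixed effect.

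**The concern.** Eligibility, approach and consent all concern the woman, and Survey Tools has the women answer. Partners then accepts an answer from someone who was not screened or recruited. Read together, some knowledge, decisional conflict and satisfaction scores could belong to a person other than the randomised participant. The available text does not say that respondent status is kept as an analysis variable or how such scores are treated.

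Three things seem to make this worse:

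- Supervision differs by group. The RA is out of the room in Groups A and B and present in Group C, so the chance that a partner answers, and that anyone notices, could differ between the groups being compared.
- The follow-up question on the partner's role means something different if the partner answers it.
- A partner's knowledge score could sit in the same record as the mother's own permission choice.

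At stake would be a shift in the knowledge contrast caused by who answered and not by what the intervention taught.

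**Working it through.** **The text, side by side.** Survey Tools describes the survey schedule in general terms. Partners comes later, deals with partners specifically, and states its rule outright. The ordinary reading is that the specific rule governs the exceptional case and the general sentence was not adjusted to it. The rule has a clear purpose: it stops the respondent changing between the hospital and telephone surveys, which would spoil any within-person comparison.

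**Is respondent status unknown?** The caller at 2-4 weeks must ask for the person who answered in hospital, so the rule cannot be carried out unless staff know who that was. Survey Tools also collects demographic and contact information on participants. The sentence on separate storage follows the mention of contact details. Whether the respondent is mother or partner does not identify anyone, so that sentence gives no reason to think the status would be unavailable to the analyst.

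**Does an analysis depend on the pairing?** The Analysis Plan relates knowledge to group and describes no model linking one person's knowledge to the permission choice. The consent card records the patient's own choice, so the permission rate is unaffected.

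**Size.** The documents give no sample size, SD, effect size or partner share, so there is no planned figure to reproduce. The Partners section reports fathers present in roughly half of the observed consent processes and involved in two thirds of those: 1/2 × 2/3 = about 1/3. That describes involvement in the discussion, not who fills in a survey, and is not used as an input.

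Assumed inputs: p, the share of surveys completed by a partner, 0.02 to 0.10; d, the partner-minus-mother difference, 0.2 to 0.5 SD, the same in each group; within-respondent SD of 1.

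1. Equal shares. Bias in the group contrast = p·d − p·d = 0.
2. SD inflation = √(1 + p(1−p)d²).
   - p = 0.02, d = 0.2: √(1 + 0.0196 × 0.04) = 1.0004
   - p = 0.05, d = 0.5: √(1 + 0.0475 × 0.25) = 1.0059
   - p = 0.10, d = 0.5: √(1 + 0.09 × 0.25) = 1.0112
3. Unequal shares. Bias = (difference in p) × d.
   - 5 points: 0.05 × 0.2 = 0.01 SD; 0.05 × 0.5 = 0.025 SD
   - Widest gap within the assumed range, 10% against 2%: 0.08 × 0.5 = 0.04 SD
4. Cost of restricting to mother-completed surveys. SE factor = 1/√(1−p).
   - p = 0.02: 1.010; p = 0.05: 1.026; p = 0.10: 1.054

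At equal p and d, the restriction in step 4 therefore costs more precision (up to 5.4%) than the mixing in step 2 (up to 1.1%). It also conditions on an event after randomisation.

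**The case for a change.** The strongest argument for a change is the difference in supervision. In Groups A and B the questionnaires follow automatically on the tablet with the RA outside the room; in Group C the RA is there. This is a mechanism, taken from the plan itself, by which partner answers could be commoner in the intervention groups. One survey item recording who answered, a count by group and a mother-only sensitivity analysis would cost little.

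Part of this stands. The asymmetry is real, the Survey Tools sentence is narrower than the Partners rule, and a careful study team would want respondent status in the data. But the documents give neither frequency nor direction, and the plausible shift is a few hundredths of an SD. Each possible change also adds little:

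- Recording who answered fills in a detail that the same-person rule already requires staff to know.
- Requiring the mother to answer would override a stated choice, in a section that considers partners' part in the decision potentially important. It would also turn some answered surveys into missing ones.
- A mother-only analysis would be a post-randomisation subset. If partner answering did differ by group, that subset would not be a randomised comparison, so it could serve as a check but not as a correction.

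The follow-up item on the partner's role is asked by telephone, where the interviewer knows who is speaking and can read the answer accordingly.

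**Conclusion.** The concern does not call for a change. What remains is a wording mismatch between Survey Tools and Partners and a handling detail that an analyst can fill sensibly: note who answered, count partner-completed surveys by group, and keep every randomised record in the intent-to-treat comparison, as the Analysis Plan already implies.

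Under the assumed ranges the bias is 0 when shares and differences are equal across groups, 0.01 to 0.025 SD for a 5-point imbalance, and 0.04 SD at the widest gap considered. The SD inflation is 1.0004 to 1.011. None of these inputs comes from the documents. A much larger imbalance in partner answers would alter the conclusion, but nothing in the plan points to one. Since some front matter and the consent pages were not available, the absence of a recording rule can be stated only for the text that could be read.
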